3.6.3 Absolute Change in Body Weight

The statistical analysis for absolute change in weight will be similar to the analysis for percent change in body weight (Section 3.6.2).

3.6.4 Proportion of Subjects Exhibiting Significant Weight Gain

A subject will be considered as exhibiting significant weight gain if he or she has a body weight change of $\geq 5\%$, $\geq 7\%$ or $\geq 10\%$ from baseline.

The proportion of subjects with significant weight gain will be estimated at each visit by the treatment group. Pooled and individual ALKS 3831 treatment group will be compared with placebo [olanzapine alone] group, and the difference with 95% CI will be reported for each comparison. It will be based on the observed values. A Cochran-Mantel-Haenszel (CMH) option will be used to make adjustment for the olanzapine lead-in period weight change strata. A sample of SAS implementation code is provided below (assuming $\geq 7\%$ weight gain is coded 1 and $< 7\%$ weight gain is coded 2 for the responder variable).

```
proc freq data=datain;
  tables strata*trt01p*responder/CMH;
  where trt01p in ('ALKS3831' 'Placebo')
  and avisit='Week 12';
run;
```

The proportion of subjects with significant weight gain based on observed cases without imputation will also be summarized at each visit by treatment group for Part A and Part B.

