5. INTRODUCTION

5.1. Background

Olanzapine is regarded as one of the most effective antipsychotics with well-recognized efficacy and other advantages such as decreased incidence of extrapyramidal symptoms. However, it also has safety and tolerability limitations which have been demonstrated to affect compliance and retention of patients on olanzapine therapy [Lieberman, 2005]. In particular, results of the CATIE (Clinical Antipsychotic Trials of Intervention Effectiveness) study identify olanzapine as an effective atypical antipsychotic agent associated with the highest weight gain (4.2 kg over up to 18 months of treatment and an overall >7% body weight in 30% of subjects) and a comparatively higher discontinuation rate due to increases in body weight and metabolic effects than other antipsychotic agents [Lieberman, 2005]. Further, it is estimated that between 40-60% of people with schizophrenia abuse alcohol and/or illicit drugs [Lubman, 2010], and these “dual diagnosis” patients have worse outcomes on a variety of measures [Batki, 2009; Dixon 1999].

ALKS 3831 is a combination drug under investigation for treatment of schizophrenia. The principle active component in ALKS 3831 is olanzapine. The other active component is samidorphan, a new chemical entity that clinical studies have shown to limit the weight gain caused by olanzapine alone. This effect was first seen in a proof-of-concept study conducted in healthy adults (Study ALK33-301). This effect appears to be specific to antipsychotic weight gain because samidorphan did not cause meaningful changes in weight when administered as a single agent in adults with binge eating disorder (Study ALK33-101).

As stated previously, despite being regarded as one of the most effective antipsychotics for the treatment of schizophrenia, safety and tolerability limitations have affected compliance and retention of patients on olanzapine therapy. As a result, many patients are switched from olanzapine to other antipsychotics to address tolerability issues even if the alternative antipsychotic is regarded as less effective. The presence of samidorphan in ALKS 3831 is to enhance the benefit and decrease the risk of the principal ingredient, olanzapine.

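### The Day 92 weight-gain proportion is compared on observed weights only, with no analysis that uses dropouts' earlier weights, and the sample code does not produce the promised difference with 95% CI

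*SAP*

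**What the plan says.** Protocol 11.2 lists the proportion with significant weight gain among the secondary endpoints. SAP 3.6.4 estimates it at each visit, compares pooled and individual ALKS 3831 groups with olanzapine alone, and promises that "the difference with 95% CI will be reported for each comparison". On the data used: "It will be based on the observed values". On stratification: "A Cochran-Mantel-Haenszel (CMH) option will be used to make adjustment for the olanzapine lead-in period weight change strata". A closing sentence adds that the proportion "based on observed cases without imputation will also be summarized at each visit", for Parts A and B.

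The sample code crosses stratum, treatment and responder status with the CMH option alone, and selects records with "and avisit='Week 12".

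Three other places bear on this:
- **SAP 3.6.2 to 3.6.3:** percent weight change has an MMRM, a LOCF ANCOVA and a linear mixed model. Absolute change is handled similarly. Nothing extends this to the proportion.
- **SAP 3.11.1.3 and Table 8:** an early-termination value within 7 days of the last samidorphan/placebo dose is mapped to the visit whose window contains it. The Visit 13 window is Days 86-98.
- **Protocol 5.1:** a cited trial found for olanzapine a "comparatively higher discontinuation rate due to increases in body weight and metabolic effects" than for other antipsychotics.

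**The concern.** A proportion taken from subjects with a Day 92 weight is unbiased only if, within arm and stratum, those who leave would have gained weight as often as those who stay. The sponsor's own rationale gives reason to doubt this: Protocol 5.1 links olanzapine discontinuation to weight and metabolic effects, and Protocol 5.3 hopes that less weight gain will improve retention. Missingness could therefore depend on both the outcome and the arm. The plan has no second analysis of this endpoint that would show whether it does. The closing sentence of 3.6.4 again uses observed cases, and its wording leaves unclear whether the main comparison was meant to differ. The subgroup analyses of the same endpoint in SAP 3.6.5 inherit the gap.

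The second issue is reporting. The effect measure that the text promises is not what the specified option prints, so the estimator and the interval method are left to the programmer.

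**Working it through.** **Plan's own figure.** There is none for this endpoint. The stated power concerns PANSS, and the only stated dropout rate, 20%, is before randomization. The sizes below are therefore illustrations.

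**Who is missing at Day 92.** A subject who stops on, say, Day 60 has the termination weight mapped to Visit 11 (Days 58-71). That subject counts in the Visit 11 proportion and is absent at Visit 13. Weight is scheduled at every visit (Protocol Table 1), so earlier weights exist but do not enter the Day 92 proportion.

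**Size of a possible bias.** Let p be the true Day 92 proportion of gainers, and dG and dN the dropout among gainers and non-gainers. Then

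observed rate = p(1 − dG) / [p(1 − dG) + (1 − p)(1 − dN)].

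Inputs:
- p = 30% on olanzapine alone. This borrows the rate of >7% gain in Protocol 5.1, which comes from treatment of up to 18 months, so it is an assumption at 12 weeks.
- p = 15% on ALKS 3831, assumed.
- dN = 20% in both arms, assumed.

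| dG placebo / ALKS 3831 | Placebo observed | ALKS 3831 observed | Difference (true 15.0) |
|---|---|---|---|
| 20% / 20% | 0.24/0.80 = 30.0% | 0.12/0.80 = 15.0% | 15.0 |
| 30% / 30% | 0.21/0.77 = 27.3% | 0.105/0.785 = 13.4% | 13.9 |
| 40% / 40% | 0.18/0.74 = 24.3% | 0.09/0.77 = 11.7% | 12.6 |
| 50% / 50% | 0.15/0.71 = 21.1% | 0.075/0.755 = 9.9% | 11.2 |
| 40% / 20% | 24.3% | 15.0% | 9.3 |
| 20% / 40% | 30.0% | 11.7% | 18.3 |

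If the true rate is 30% in both arms, the 40%/20% pattern shows 24.3% against 30.0%, a spurious 5.7 points against ALKS 3831. The 20%/40% pattern gives 5.7 points in its favour. With an assumed ALKS 3831 rate of 20% (true difference 10.0), equal gainer dropout of 30%, 40% and 50% in both arms gives 9.3, 8.5 and 7.6 points.

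**What the code prints.** For stratified 2×2 tables, the CMH option gives association tests and common odds and risk ratios. A made-up example, by stratum: placebo 3/20, 7/25, 11/25; ALKS 3831 4/60, 10/75, 18/75.
- Mantel-Haenszel odds ratio: (0.85 + 1.80 + 2.52)/(2.10 + 4.55 + 6.27) = 5.17/12.92 = 0.40.
- Risk ratio: (1.0 + 2.5 + 4.5)/(2.25 + 5.25 + 8.25) = 8/15.75 = 0.51.
- Risk difference, with weights n0·n1/N of 15, 18.75 and 18.75: (−1.25 − 2.75 − 3.75)/52.5 = −14.8 points, 95% CI −26.2 to −3.3. This needs a separate calculation.

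Nor can the difference be recovered from the ratio. An odds ratio of 0.41 with stratum placebo rates of 5/10/20%, 15/30/45% or 30/50/70% gives equally weighted differences of −6.4, −14.3 or −18.9 points.

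**Visit label.** Day 92 − Day 8 = 84 days = 12 weeks of double-blind treatment. The protocol schedule labels Day 92 as Visit 13, Week 13. SAP 3.11.1.1 ties analysis visits to nominal eCRF visits, and Table 8 uses Visit 13.

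**The case against.** The strongest reply is that dropout is already handled where it matters most. The continuous weight outcomes have an MMRM and LOCF support, so the gap is confined to a dichotomised version in a Phase 2 study. The termination rule also recovers some subjects and lets dropouts count at earlier visits, and the code is only a sample. All of this is correct and limits the consequence. It does not supply a Day 92 responder analysis that uses the weights of those who stopped before Day 86, nor does it name an estimator for the difference. The choice of multiple imputation over LOCF is partly preference.

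A reader might infer four stronger things that the documents do not support:
- **That everyone without a Visit 13 attendance is dropped.** The termination mapping for Days 86-98 contradicts this.
- **That the protocol establishes weight gain as a cause of dropout here.** Protocol 5.1 compares drugs in a trial of up to 18 months and names weight and metabolic effects together. It says nothing about gainers against non-gainers, or about arms, over 12 weeks.
- **That the bias must hide a benefit.** The last row of the table goes the other way.
- **That the code contradicts a promised stratum-adjusted difference, or picks the wrong visit.** The SAP never joins adjustment and difference in one phrase, so an unadjusted difference beside a CMH test also fits the text. The visit label can be read as weeks since randomization.

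**Conclusion.** The point holds as a gap in the plan, and no bias has been demonstrated. Two things follow from the text alone: no analysis of the Day 92 proportion uses the earlier weights of subjects who leave before the Visit 13 window, and the difference with its interval has no specified estimator under either reading of 3.6.4. The size is conditional. Under the assumed 30% and 15%, the bias is nil with equal dropout in gainers and non-gainers. The observed difference is 9.3 to 13.9 points, against 15.0, when gainers leave more often in both arms or only on placebo, and 18.3 when they do so only on ALKS 3831. Those figures rest on assumed rates and on 20% dropout among non-gainers. The visit label is a naming inconsistency. The change is worth making because it is cheap and the endpoint is a named secondary.

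**What to change.** In SAP 3.6.4:
- Make the Day 92 comparison use multiple imputation of missing weight, with the planned weight MMRM terms (lead-in strata, treatment, visit, treatment-by-visit, baseline weight). Classify each completed data set against the thresholds and combine the results.
- Keep the observed-case analysis as supportive.
- Name the effect measure as a Mantel-Haenszel stratified common risk difference with 95% CI, and add the matching request to the code beside the CMH test.
- Replace the visit label in the code with Visit 13/Day 92.

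The cost is SAP wording and modest programming, with no new data. The imputation relies on missing at random, which the weight MMRM already assumes. This is weaker than what observed cases require, because it conditions on each subject's earlier weights.

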3.6.5 Examination of Subgroups

For percent change in body weight and proportion of subjects exhibiting significant weight gain, the following subgroup analysis will be performed with similar analysis methods as described in Sections 3.6.2 and 3.6.4 when appropriate:

- Weight gain category during the olanzapine lead-in period (change ≤ 0 kg, increase >0 to <1 kg, increase ≥ 1 kg)
- BMI (<25 , ≥ 25)
- BMI (<27 , ≥ 27)
- Gender (male, female)
- Age (≥ 18 - ≤ 39 , ≥ 40 - ≤ 50)
- Region (US, non-US)

3.6.6 Change in Clinical Global Impression - Severity

The CGI-S is a 7-point scale ranging from 1=normal to 7=extremely ill. .

The change from baseline to Day 92 in CGI-S will be carried out using the MMRM model including the weight change strata in olanzapine lead-in period, treatment group, visit, and a treatment group-by-visit interaction term as categorical fixed effects; baseline CGI-S value will be included as a covariate.

A summary of CGI-S at each visit will be presented using descriptive statistics for Part A and Part B.

3.6.7 Efficacy Analysis for the Additional Endpoints

Unless otherwise specified, exploratory efficacy endpoints will be summarized in descriptive statistics by visit and treatment groups. They include change in waist circumference, change in IWQOL-Lite scales (total score, physical function, self-esteem, sexual life, public distress, and work), change in PSP, change in FCI (total score, high fat, sweets, carbohydrates/starches, fast-food fats), and change in alcohol and drug use.

For change in waist circumference, MMRM will also be conducted, including the weight change strata in olanzapine lead-in period, treatment group, visit, and treatment group-by-visit interaction term as categorical fixed effects; baseline value will be included as a covariate.

For IWQOL-Lite scale is a 31-item self-report measure of obesity-specific quality of life. The

IWQOL-Lite provides an overall total score as well as scores on five domains: (1) physical function, (2) self esteem, (3) sexual life, (4) public distress, and (5) work. The raw scores will be transformed as follows [4]. The transformed scores range from 0 to 100, with 100 representing the best and 0 the most impaired quality of life.

$$\text{Transformed Score} = \frac{\text{maximum theoretical score} - \text{actual score}}{\text{test score range}} \times 100$$

For FCI, total scores and subscores for high fat, sweets, carbohydrates/starches and fast-food fats will be calculated as following:

FCI Total score = average response for items 1 to 28. Possible range is 1-5.

High fat subscore=average response for items 3, 4, 6, 10, 15, 19, 26 and 27. Possible range is 1-5.

Sweets subscore=average response for items 1, 8, 13, 16, 17, 23, 24 and 25. Possible range is 1-5.

Carbohydrates/starches subscore=average response for items 5, 9, 12, 14, 18, 21, 22 and 28. Possible range is 1-5.

Fast-food fats subscore=average response for items 2, 7, 11 and 20. Possible range is 1-5.

For alcohol use as assessed by TLFB, percent of drinking days for the prior 30 days will be summarized at each visit.

Number and percentage of subjects with any drug use at each scheduled time point will be summarized by treatment group. It will also be summarized for individual drugs.

3.7 SAFETY ANALYSIS

3.7.1 General Considerations

Safety analyses will be primarily based on Safety Populations and include AEs, clinical laboratory assessments (hematology, blood clinical biochemistry, and urinalysis), vital signs, ECG parameters, and data from C-SSRS surveys in Part A and Part B treatment periods.

Safety analyses will be performed on observed data, and no missing values will be imputed.

3.7.2 Adverse Events

Reported AE terms will be coded by System Organ Class (SOC) and Preferred Term (PT) using the Medical Dictionary for Regulatory Activities (MedDRA®) version 15.0. The verbatim term will be included in the AE listings.

3.7.2.1 Treatment-Emergent Adverse Event

An AE will be considered as treatment-emergent AE (TEAE) if the event is newly occurring or after the first dose of study drug. AEs will be identified as emerging in the following periods:

- TEAEs during the olanzapine lead-in period
- TEAEs for the Part A placebo-controlled period
- TEAEs for the Part B ALKS 3831 treatment period
- TEAEs for the Part A placebo-controlled period and Part B ALKS 3831 treatment period combined
- TEAEs during the follow-up period:
 - after discontinuation in the olanzapine lead-in period
 - after discontinuation in Part A placebo-controlled period
 - after discontinuation or completion of Part B ALKS 3831 treatment period

All AEs will be listed by subject, but only TEAEs will be included in the summary tables. Summary tables will be produced for the specified periods above.

An overall summary of TEAEs such as all TEAEs, treatment-related TEAEs, TEAEs leading to study discontinuation, serious TEAEs, serious and treatment-related TEAEs, and TEAEs resulting in death will be summarized for each treatment group.

In addition, the following summary tables will be produced:

- TEAEs experienced by $\geq 2\%$ of subjects in any treatment group for Part A placebo-controlled period, Part B ALKS 3831 treatment period, and combined period
- Treatment-related TEAEs experienced by $\geq 2\%$ of subjects in any treatment group for Part A placebo-controlled period, Part B ALKS 3831 treatment period, and combined period

- The number and percentage of subjects with TEAEs by treatment group, SOC, PT, and severity for Part A placebo-controlled period, Part B ALKS 3831 treatment period, and combined period

A subject with the same AE more than once will be counted once in the number and percentage of subjects calculation for that AE. Similarly, if a subject has more than one AE in an SOC, the subject will be counted only once in the total number of subjects with an AE for that SOC. If a subject has the same AE on multiple occasions, the highest severity (severe>moderate>mild) or drug relationship (definitely related>probably related>possibly related>probably not related>definitely not related) recorded for the event will be presented.

An AE that occurs after a subject provides informed consent but before the first dose of study drug will be considered as a pre-treatment AE.

3.7.2.2 Deaths, Serious and Other Significant AEs

The number and percentage of subjects with at least one treatment emergent SAE will be summarized by System Organ Class, and Preferred Term for each treatment group for Part A placebo-controlled period, Part B ALKS 3831 treatment period, and combined period. Subjects with AEs leading to study discontinuation will be summarized similarly. Subjects who died during the study will be listed.

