13.4. Relationship to Study Drug

The assessment of study drug relationship to each AE will be reported on the appropriate source document (and SAE form, in the event of an SAE) by the PI (or designated investigator) according to his/her best clinical judgment. The criteria listed in [Table 4](#) should be used to guide this assessment. Please note that not all criteria must be present to be indicative of a particular drug relationship. All study drugs are considered "test drugs" for the purposes of the definitions listed in the table. However, relationship and action taken will be separated out in the EDC to assess for olanzapine and samidorphan/placebo separately. The PI (or designated investigator) can attribute relationship to olanzapine, samidorphan/placebo or both.

Table 4: Causality Guidelines

Relationship¹	Criteria for assessment
Definitely related	
There is evidence of exposure to the test drug. AND The temporal sequence of the AE onset relative to administration of the test drug is reasonable. The AE is more likely explained by the test drug than by another cause. Dechallenge (if performed) is positive. Rechallenge (if feasible) is positive. The AE shows a pattern consistent with previous knowledge of the test drug or test drug class.

Probably related	
There is evidence of exposure to the test drug. AND The temporal sequence of the AE onset relative to administration of the test drug is reasonable. The AE is more likely explained by the test drug than by another cause. Dechallenge (if performed) is positive.

Possibly related	
There is evidence of exposure to the test drug. AND The temporal sequence of the AE onset relative to administration of the test drug is reasonable. The AE could have been due to another equally likely cause. Dechallenge (if performed) is positive.

Probably not related	
There is evidence of exposure to the test drug. AND There is another more likely cause of the AE. Dechallenge (if performed) is negative or ambiguous. Rechallenge (if performed) is negative or ambiguous.

Definitely not related	
The subject did not receive the test drug. OR Temporal sequence of the AE onset relative to administration of the test drug is not reasonable. OR There is another obvious cause of the AE.

¹ Relationship will be assessed twice: once for olanzapine and once for samidorphan/placebo

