14.6. Safety and Tolerability Analyses

Reported AE terms will be coded using the Medical Dictionary for Regulatory Activities (MedDRA[®]) preferred terms and system organ classes. Descriptive summary statistics will be provided for AEs, laboratory tests, and vital signs and will include mean, SD, median, minimum and maximum for continuous variables and number and percent for categorical variables.

The incidence of AEs, including clinically significant abnormal laboratory tests or ECG values, will be summarized for each treatment group and overall, by severity and by relationship to study drug. The summary tables will include the number and percent of subjects with AEs overall, by

system organ class, and by preferred terms within each system organ class. AEs resulting in treatment discontinuation or modification will be identified.

Laboratory tests will be summarized by visit for the absolute value itself and for change from baseline. Tables showing the shift from baseline will also be presented.

ECG findings will be summarized by visit. Concomitant medications will be categorized and presented using the World Health Organization (WHO) drug Anatomical Therapeutic Chemical (ATC) classification system.

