3.10 DEVIATIONS FROM THE PROTOCOL AND SPECIFIED ANALYSES

There are no deviations from the protocol specified analyses.

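### The SAP plans no by-arm rate of AEs leading to interruption or dose change of either drug, and its treatment-related category names no drug although attribution is recorded per drug

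*SAP*

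**What the plan says.** Protocol 13.4 has each AE's causality judged twice, once per drug, and adds that "relationship and action taken will be separated out in the EDC to assess for olanzapine and samidorphan/placebo separately". Protocol 13.6 repeats the double assessment for SAE reports. In its analysis section (14.6), the protocol plans AE summaries by relationship to study drug, without saying per drug, and then states: "AEs resulting in treatment discontinuation or modification will be identified".

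SAP 3.7.2.1 gives the overall TEAE summary as all TEAEs together with "treatment-related TEAEs, TEAEs leading to study discontinuation, serious TEAEs, serious and treatment-related TEAEs, and TEAEs resulting in death". It adds one treatment-related table for events reaching 2% in any group, for Part A, Part B and both combined. Its counting rule for repeated events is that the highest severity or "drug relationship (definitely related>probably related>possibly related>probably not related>definitely not related) recorded for the event will be presented". SAP 3.7.2.2 adds the SAE table and then: "Subjects with AEs leading to study discontinuation will be summarized similarly". The SAP's AE sections do not mention action taken, interruption, dose change or discontinuation of one drug. SAP 3.10 says: "There are no deviations from the protocol specified analyses".

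**The concern.** Every subject takes olanzapine at a dose left to the investigator (protocol 8.3.20), with blinded samidorphan or placebo added. An AE can therefore lead to a change or interruption of olanzapine while the subject stays in the study. Protocol 8.4.4 also describes a situation in which study drug is withheld (opioid analgesia needed before dosing) and does not call for withdrawal there. Such an event is counted as a TEAE, but no planned table shows that it led to action on treatment.

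The relatedness tables have a separate problem. Each AE carries two attributions, and the SAP does not say which one, or which combination, makes an event treatment-related. Safety and tolerability of the combination is the second study objective, in a dose-ranging study of samidorphan. These are the tables a reader would consult to see how often side effects led to a change in treatment and which drug was blamed.

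**Working it through.** No figure in the documents is at issue, so the check sets the texts side by side and then sizes the dilution under stated assumptions.

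**1. Consequences for treatment**

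| Item | Protocol | SAP |
|---|---|---|
| AE leading to study exit | Withdrawal and ET visit (7.3) | Tabulated (3.7.2.1, 3.7.2.2) |
| AE leading to stopping or changing treatment | To be identified (14.6) | Not mentioned in the AE sections |
| Action taken, per drug | Recorded in the EDC (13.4) | Not used in any named table |
| Exposure, per drug | – | Split by drug (3.5) |
| Average olanzapine dose | – | Summarised for Parts A and B (3.5) |

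The average-dose summary would tend to show a systematic difference in olanzapine dose between arms. It does not say how many subjects had a change because of an AE, or which AE.

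**2. Relatedness**

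Take an event judged related to olanzapine and not to samidorphan/placebo. It is treatment-related if the flag means either drug. It is not if the flag means both drugs, or samidorphan/placebo only. All three programs would comply with the SAP. The highest-relationship rule does not settle this, because it covers one AE occurring on several occasions, not two attributions of one occurrence.

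**3. Size of the dilution if the flag means either drug (illustration only)**

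Assumed rates, none of them from the documents:
- samidorphan/placebo-attributed AEs in 15% of subjects on samidorphan and 5% on placebo
- olanzapine-attributed AEs in the same proportion *o* of every arm, varied from 10% to 50%
- the two attributions independent

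Related to either drug = 1 − (1 − *o*)(1 − *s*). The difference between arms is then (1 − *o*)(0.15 − 0.05).

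At *o* = 10%: 1 − 0.90 × 0.85 = 23.5% versus 1 − 0.90 × 0.95 = 14.5%.

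| *o* | Samidorphan | Placebo | Difference (points) | Ratio |
|---|---|---|---|---|
| Samidorphan/placebo attribution only | 15.0% | 5.0% | 10.0 | 3.0 |
| 10% | 23.5% | 14.5% | 9.0 | 1.62 |
| 20% | 32.0% | 24.0% | 8.0 | 1.33 |
| 30% | 40.5% | 33.5% | 7.0 | 1.21 |
| 40% | 49.0% | 43.0% | 6.0 | 1.14 |
| 50% | 57.5% | 52.5% | 5.0 | 1.10 |

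The undivided category shrinks the contrast but does not remove it. The comparison of all TEAEs by randomised arm does not depend on attribution and is untouched.

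**4. Where attribution matters**

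In Part A all four arms take olanzapine, so each samidorphan dose against olanzapine plus placebo isolates samidorphan. In Part B every subject takes samidorphan and the former placebo group moves to the highest dose (SAP 1.2). The dose groups can still be compared with one another, but there is no concurrent samidorphan-free arm. Investigator attribution is then one of the few ways left to separate the two drugs.

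**The case against.** A reader might infer that samidorphan's tolerability is masked by olanzapine. For Part A the documents do not support that. All TEAEs, TEAEs by organ class, term and severity, SAEs and study discontinuations are compared by blinded randomised arm against olanzapine plus placebo. Sedation has its own category (SAP 3.7.2.2.1), so sedation handled by changing olanzapine would still be counted. Only its link to the change would be missing.

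A reader might also infer that the SAP deletes a promised per-drug analysis and that SAP 3.10 is therefore false. Protocol 13.4 governs collection, and 14.6 promises only relationship to study drug. It says that AEs leading to treatment discontinuation or modification will be identified, not tabulated. The SAP lists all AEs by subject and presents all source data as listings, and its list of overall summary items is not worded as exhaustive. The table shells are in a separate document (SAP 4). A listing could meet the protocol's wording, although the SAP names no action-taken field in it and a listing gives no rate by arm.

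Two further points stand. The protocol describes no route for permanently stopping samidorphan while staying in the study, and samidorphan dose is fixed by arm. Treatment and study discontinuation may therefore largely coincide, leaving olanzapine changes and temporary interruptions as the main gap. And blinded investigators must divide blame between two drugs taken at the same time (protocol 9.1), so per-drug attribution is imprecise.

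**Conclusion.** The point holds in a limited form. The SAP names no summary, by arm, of AEs leading to interruption or dose change of either drug without study exit. Its treatment-related category is also undefined when each AE carries two attributions. Neither gap hides the randomised Part A comparison. Nor would the missing events be reported as a zero rate: no such row is planned, and the events stay in the TEAE tables.

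If treatment-related is read as either drug, the assumed 10-point contrast falls to between 9.0 and 5.0 points, and the ratio from 3.0 to between 1.62 and 1.10. That range rests on assumed rates and independent attributions, and shows direction and scale only. The loss matters most in Part B. Whether SAP 3.10 is wrong cannot be settled from these documents. This is an inexpensive improvement to safety reporting and does not threaten the primary analysis.

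**What to change.** In SAP 3.7.2.1 and 3.7.2.2:

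1. Tabulate by arm, for Part A and Part B, TEAEs leading to discontinuation, interruption or dose change, separately by action taken with samidorphan/placebo and by action taken with olanzapine.
2. Define treatment-related as related to either drug. Also present the related and serious related tables separately for each drug.
3. Keep the study-discontinuation table.

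If the sponsor prefers not to add these tables, SAP 3.10 should say how the commitment in protocol 14.6 is met or record the omission.

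The cost is SAP wording and a few extra tables from fields the protocol already requires, with no new data. Because blinded attribution between two co-administered drugs is imprecise, the per-drug tables should be labelled as supplements to the all-TEAE comparison by arm.
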